#### 4. Section 1 – Type and Number of Subjects

The study will enroll adult subjects with RR rel/ref MM, who have undergone stem cell transplant, or who are considered transplant ineligible. Subjects must have been, and who have been previously treated with at least 32 prior lines that include the following:-, containing 3 classes of anti-myeloma drugs: an alkylating agent, AND an immunomodulatory imide drug -IMiD (eg i.e. lenalidomide or pomalidomide), AND a

proteasome inhibitor -PI (eg i.e. bortezomib, ixazomib or carfilzomib) and an anti-CD38 antibody alone or in combination. Line of therapy are defined by consensus panel of the International Myeloma Workshop [Rajkumar, 2011]. In addition, subject must be progressing on, or within 60 days since the most recent therapy (as defined by IMWG).

Overall, it is estimated that up to 408 evaluable subjects will be enrolled in this two-part study (up to 128 in Part 1, and 2830 in Part 2).

**Reason for change:** Revision of the targeted population and number of subjects due to FDA comments and adjustment to proposed dose level due to FDA comments.

## 5. Section 1 – Key Inclusion Criteria

Subjects eligible for enrolment in the study must meet all of the following criteria:

- Provide signed written informed consent, which includes compliance with the requirements and restrictions listed in the consent form
- Male or female, 18 years or older (at the time consent is obtained)
- Eastern Cooperative Oncology Group (ECOG) performance status of 0 or 1.
- Have confirmed diagnosis of Multiple Myeloma and have undergone stem cell transplant, or are considered transplant ineligible
- Histologically or cytologically confirmed diagnosis of MM as defined according to IMWG, 2014 [Rajkumar, 2014], and
  - Has undergone stem cell transplant or is areconsidered transplant ineligible, and
  - Has been treated with at least 32 prior lines of prior anti-myeloma treatments, including 3 classes of drugs: an alkylating agent, AND an IMiD (eg. lenalidomide or pomalidomide), AND a proteasome inhibitor (eg., bortezomib, ixazomib or carfilzomib) and an anti-CD38 antibody, alone or in combination. Line of therapy are defined by consensus panel of the International Myeloma Workshop [Rajkumar, 2011]. In addition, subject must be progressing on, or within 60 days since the most recent treatment (as defined in International Myeloma Working Group Uniform Response Criteria, 2011 [Rajkumar, 2011])
- In addition to the criteria above, subjects in Part 2 must have Has measurable disease defined as one of the following:
  - a) Serum M-protein  $\geq 0.5$  g/dL ( $\geq 5$  g/L).
  - b) Urine M-protein  $\geq 200$  mg/24h.
  - c) Serum FLC assay: Involved FLC level  $\geq 10$  mg/dL ( $\geq 100$  mg/L) and an abnormal serum free light chain ratio ( $<0.26$  or  $>1.65$ )
  - d) Biopsy proven plasmacytoma (should be measured within 28 days of Screening Visit)
- Subjects with a history of autologous stem cell transplant (SCT) are eligible for study participation provided the following eligibility criteria are met:
  - a) Transplant was  $> 100$  days prior to study enrolment.
  - b) No active infection (s).
  - c) Subject meets the other eligibility criteria outlined in this protocol.

- ~~Subjects after prior allo SCT are allowed if the allo transplant was performed  $\geq 5$  years ago, and if subject has no active graft versus host disease requiring treatment.~~
- Subject has adequate organ system functions defined in the Table below:

System	Laboratory Values
Hematologic	
Absolute neutrophil count (ANC) 	$\geq 1.0 \times 10^9/L$
Hemoglobin	$\geq 8.0 \text{ g/dL}$
Platelets	$\geq 75 \times 10^9/L$
Coagulation	
INR	$\leq 1.5 \text{ ULN}$
aPTT	$\leq 1.5 \times \text{ULN}$
Hepatic	
Total bilirubin	$\leq 1.25 \times \text{ULN}$ (Isolated bilirubin $>1.25 \times \text{ULN}$ and $\leq 3 \times \text{ULN}$ is acceptable if bilirubin is fractionated and direct bilirubin $<35\%$ )
AST and ALT	$\leq 4.25 \times \text{ULN}$
Renal	
eGFR 	$\geq 450 \text{ mL/min}$
Albuminuria Spot urine (albumin creatinine ratio)	$\leq 500 \text{ mg/g (56 mg/mmol) 24 hr}$
Cardiac	
LVEF (Echo)	$\geq 50\%$
QTcF interval 	$< 470 \text{ msec}$

 
Without Growth factor support for the past 14 days, excluding erythropoietin
 
As calculated by Modified Diet in Renal Disease (MDRD) formula
 
The QT interval should be corrected for heart rate by Fridericia's formula (QTcF)
 
	

- All prior treatment-related toxicities (defined by National Cancer Institute-Common Toxicity Criteria for Adverse Events (NCI-CTCAE), version 4.03, 2010) [NCI, 2010] must be  $\leq$  Grade 1 at the time of enrollment except for alopecia, and Grade 2 neuropathy.
- A female subject is eligible to participate if she is not pregnant or breastfeeding, and at least one of the following conditions applies:
  - Is not a woman of childbearing potential (WOCBP)  
OR
  - Is a WOCBP and using a contraceptive method that is highly effective (with a failure rate of  $<1\%$  per year), preferably with low user dependency, as described in Appendix 8 during the intervention period and for at least 120 days after the last dose of study intervention and agrees not to donate eggs (ova, oocytes) for the purpose of reproduction during this period. The investigator should evaluate the effectiveness of the contraceptive method in relationship to the first dose of study intervention.

A WOCBP must have a negative highly sensitive serum pregnancy test (as required by local regulations) within 72 hours before the first dose of study intervention.

Additional requirements for pregnancy testing during and after study intervention are located in Appendix 8.

The investigator is responsible for review of medical history, menstrual history, and recent sexual activity to decrease the risk for inclusion of a woman with an early undetected pregnancy.

- Male Subjects:

- Male subjects are eligible to participate if they agree to the following during the intervention period and for at least 140 days after the last dose of study intervention:
  - Refrain from donating sperm  
PLUS either:
    - Be abstinent from heterosexual intercourse as their preferred and usual lifestyle (abstinent on a long term and persistent basis) and agree to remain abstinent

OR
- Must agree to use contraception/barrier as detailed below
  - Agree to use a male condom and female partner to use an additional highly effective contraceptive method with a failure rate of <1% per year as described in Appendix 8 when having sexual intercourse with a woman of childbearing potential who is not currently pregnant.

~~A female subject is of non childbearing potential or women of childbearing potential must have a negative serum pregnancy test within 72 hours prior to the first dose of study treatment and agree to use effective contraception during the study and for 120 days following the last dose of study treatment.~~

~~Men with a female partner of childbearing potential must have either had a prior vasectomy or agree to use effective contraception from the time of first dose of study treatment until 140 days after the last dose of study treatment to allow for clearance of any altered sperm.~~

**Reason for change:** Revision of Inclusion Criteria due to update in line of therapy and update of contraception language.

## 6. Section 1 – Key Exclusion Criteria

A subject will not be eligible for inclusion in this study if any of the following criteria apply:

- Systemic anti-myeloma therapy or an investigational drug within ≤14 days or five half-lives, whichever is shorter, preceding prior to the first dose of study drug or
- Plasmapheresis within 7 days prior to the first dose of study drug

- Prior treatment with a monoclonal antibody within 30 days of receiving the first dose of study drugs
- Has received prior therapy with an anti-PD-1, anti-PD-L1, or anti PD-L2 agent or with an agent directed to another stimulatory or co-inhibitory T-cell receptor (e.g., CTLA-4, OX 40, CD137) and was discontinued from that treatment due to a Grade 3 or higher immune related adverse event (irAE)
- Current corneal epithelial disease except mild punctate keratopathy
- Use of an investigational drug within 14 days or five half-lives, whichever is shorter, preceding the first dose of study drug
- History of an allogeneic stem cell transplant within last 5 years
- Evidence of active mucosal or internal bleeding
- Any major surgery within the last four weeks prior to the first dose of study therapy
- Presence of active renal condition (infection, requirement for dialysis or any other condition that could affect subject's safety). Subjects with isolated proteinuria resulting from MM are eligible, provided they fulfil criteria for the adequate renal functions defined in the inclusion criteria
- Any serious and/or unstable pre-existing medical, psychiatric disorder or other conditions (including lab abnormalities)
- Has received prior radiotherapy within 2 weeks of start of study therapy. Subjects must have recovered from all radiation-related toxicities, not require corticosteroids, and not have had radiation pneumonitis. A 1-week washout is permitted for palliative radiation (<2 weeks of radiotherapy) to non-central nervous system (CNS) disease
- History of (non-infectious) pneumonitis that required steroids or current pneumonitis
- Current active liver or biliary disease per investigator assessment defined by the presence of ascites, encephalopathy, coagulopathy, hypoalbuminemia, esophageal or gastric varices, persistent jaundice, or cirrhosis. Note: Stable chronic liver disease (with the exception of Gilbert's syndrome or asymptomatic gallstones or otherwise stable chronic liver disease per investigator's assessment) or hepatobiliary involvement of malignancy is acceptable if subject otherwise meets entry criteria
- Malignancies other than disease under study are excluded, except for any other malignancy from which the participant has been disease-free for more than 2 years and, in the opinion of the principal investigators and GSK Medical Monitor, will not affect the evaluation of the effects of this clinical trial treatment on the currently targeted malignancy (RRMM). In addition, subjects with curatively treated non-melanoma skin cancer are allowed
- Has known active CNS metastases and/or carcinomatous meningitis. Subjects with previously treated brain metastases may participate provided they are radiologically stable, i.e., without evidence of progression for at least 4 weeks by repeat imaging (note that the repeat imaging should be performed during study screening), clinically stable and without requirement of steroid treatment for at least 14 days prior to first dose of study therapy. Subjects with previous or concurrent malignancies are allowed only if the second tumor is not contributing to the subject's illness.

- Evidence of any cardiovascular risk defined in the protocol
  - QTcF interval  $\geq$ 470 msec
  - Evidence of current clinically significant uncontrolled arrhythmias;
    - including clinically significant electrocardiogram (ECG) abnormalities including 2nd degree (Type II) or 3rd degree atrioventricular (AV) block.
  - History of myocardial infarction, acute coronary syndromes (including unstable angina), coronary angioplasty, or stenting or bypass grafting within six months of Screening.
  - Class III or IV heart failure as defined by the New York Heart Association functional classification system (Appendix 4)
  - Uncontrolled hypertension
  - Presence of cardiac pacemaker (or defibrillator) with a predominantly ventricular paced rhythm, limiting ECG/QTcF analysis.
  - Abnormal cardiac valve morphology ( $\geq$ Grade 2) documented by echocardiogram (subjects with grade 1 abnormalities CCI [REDACTED] can be entered on study). Subjects with moderate valvular thickening should not be entered on study.
- Known immediate or delayed hypersensitivity reaction or idiosyncrasy to drugs chemically related to GSK2857916 or pembrolizumab, or any of the components of the study treatment.
- Pregnant or lactating female
- Known active infection requiring antibiotic, antiviral, or antifungal treatment
- Known HIV infection
- Presence of hepatitis B surface antigen (HBsAg), or hepatitis B core antibody (HBcAb at screening or within 3 months prior to first dose of study treatment)
- Positive hepatitis C antibody test result or positive hepatitis C RNA test result at screening or within 3 months prior to first dose of study treatment.  
NOTE: Subjects with positive Hepatitis C antibody due to prior resolved disease can be enrolled, only if a confirmatory negative Hepatitis C RNA test is obtained  
NOTE: Hepatitis RNA testing is optional and subjects with negative Hepatitis C antibody test are not required to also undergo Hepatitis C RNA testing
- ~~Subjects with positive test for Hepatitis B surface (HBS Ag) or Hepatitis B core (HBc) antigen.~~
- ~~Subjects with positive test for hepatitis C (HCV) infection are excluded regardless of viral load (if hepatitis C antibody is positive but confirmatory PCR or RIBA test is negative, subject is eligible).~~
- ~~Current corneal epithelial disease~~
- Has received a live-virus vaccination within 30 days of planned start of study therapy.
- Active autoimmune disease that has required systemic treatment in past 2 years (i.e. with use of disease modifying agents, corticosteroids or immunosuppressive drugs). Replacement therapy (eg, thyroxine, insulin, or physiologic corticosteroid replacement therapy for adrenal or pituitary insufficiency, etc.) is not considered a form of systemic treatment.
- Has a diagnosis of immunodeficiency or is receiving chronic systemic steroid therapy (in dosing exceeding 10 mg daily of prednisone equivalent) or any other

form of immunosuppressive therapy within 7 days prior the first dose of study therapy

- Has known psychiatric or substance abuse disorders that would interfere with the subject's ability to cooperate with the requirements of the study
- Has had an allogenic tissue/solid organ transplant

**Reason for change:** Revision of Exclusion Criteria due to updates to the GSK and Merck standard language.

## 7. Section 1 – Study Treatment and Duration

[figure not shown]
### Study Treatment and Duration

Product name:	GSK2857916	Pembrolizumab
[Formulation description:]	20mg/mL, 1.5 mL/vial	100 mg/4mL
Route of Administration	Delivered as 30 min IV infusion. Refer to Study Reference Manual (SRM) for details.	Delivered as 30 min IV infusion

### Treatment Duration

GSK2857916 and pembrolizumab will be administered via intravenous (IV) infusion on day 1 of each 21-day cycle (once every 3 week Q3W-dosing schedule). Subjects enrolled in Part 1 and 2 will be treated until disease progression, intolerable toxicity, informed consent withdrawal, or for a maximum of 32 35 cycles (approximately 2 years, See Combination Treatment Schematic below).

[figure not shown]
### Old Figure:

#### Dosing:

- GSK2857916 and pembrolizumab on D1 of each cycle
- GSK2857916 first, Pembrolizumab as second iv infusion (1hr apart)
- If IRR related to GSK2857916, the pembrolizumab dosing will be delayed (up to 48 hrs)
- Max treatment duration: 32 cycles

### New Figure:

**Dosing:**

- GSK2857916 and pembrolizumab on D1 of each cycle
- GSK2857916 first, Pembrolizumab as second iv infusion (1hr apart)
- If IRR related to GSK2857916, the PD1 dosing will be delayed
- Max treatment duration: 35 cycles combination treatment

~~Subjects who achieve complete response (CR/sCR) are allowed to have early treatment discontinuation under following conditions: subjects have attained a CR/sCR and have been treated for at least 8 cycles with the combination of GSK2857916 and pembrolizumab and had at least 2 treatment cycles with both study drugs beyond the date when the initial CR is declared.~~

[figure not shown]
~~The subjects who have early treatment discontinuation will not be allowed to re-enter the study treatment at later time.~~

~~After treatment discontinuations all subjects will be followed up every 3 months for 12 months for PFS and OS. Subjects who discontinued treatment for reasons other than PD will be followed up every 3 weeks until confirmed PD, initiation of a new anticancer therapy or death. All subjects with confirmed PD will be followed for OS every 3 months until the end of study. End of study is defined as when all subjects have been followed for 36 months from first dose of study treatment or died or withdrew consent or are lost to follow-up. The next subsequent therapy will be collected for all subjects who have confirmed PD before initiation of new anticancer therapy.~~

[figure not shown]
### Part 1: Dose Escalation

Part 1 dose escalation will characterize the safety and tolerability of escalating doses of GSK2857916 in combination with 200 mg pembrolizumab to establish the RP2D. The following dose levels of GSK2857916 in combination with 200 mg pembrolizumab are planned to be studied: 1.92 mg/kg, 2.5 mg/kg (dose level [DL] 1) and 3.4 mg/kg (DL2) (as outlined in Dose Escalation Schematic for Part 1 below). Additionally, other intermediate dose levels may also be explored. Dose level 1.92 mg/kg may be tested if dose level 2.5 mg/kg is not cleared. During the dose escalation, at least 3 evaluable subjects will be studied per dose level. In Part 1, any subject who received at least one treatment cycle of the combination will be evaluated for DLTs. Subjects who have received only GSK2857916 or have been withdrawn from the study for reasons other than toxicity but prior to completion of DLT observation period will be replaced.

### Old Dose Escalation Schematic for Part 1

## New Dose Escalation Schematic for Part 1

**Reason for change:** Update to number of total cycles based on actual 24 month calendar and in line with maximum dosing from Merck language. Revisions of schematics to match revised plan. Revision of starting dose based on guidance from FDA. Removal of option to discontinue treatment if CR/sCR achieved based on program language.

### 8. Section 1 – Dose Limiting Toxicity Criteria (Part 1 only)

The DLT observation window will be 21 days (=1 cycle). Any subject in Part 1 who received at least one treatment cycle of the combination of GSK2857916 and pembrolizumab will be evaluated for DLTs using National Cancer Institute (NCI) CTCAE Version 4.03 [NCI, 2010]. In addition, for GSK2857916 treatment related corneal events, the GSK grading scale for corneal events (Appendix 9) should be used for evaluation of DLT.

A DLT is defined as an AE that meets at least one of the criteria defined below and is considered by the investigator to be clinically relevant and attributed (definitely, probably, or possibly) to the study therapy during the 21 day DLT observation period.

~~An event will be considered a DLT if its relationship to the investigational agents cannot be ruled out, occurs within the DLT reporting period, and meets one of the following criteria:~~

1. Any Grade 4 non-hematologic toxicity
2. Any Grade 3 or greater non-hematologic toxicity, with the following exceptions (i.e., the following will not be considered a DLT): Grade 3 diarrhea, nausea, or vomiting that responds to standard of care within 72 hours; Grade 3 hypertension (controlled following addition of 1 antihypertensive medication); and Grade 3 tumor lysis syndrome not resolving with appropriate supportive treatment within 48 hours, or resulting in a delay in initiating cycle 2 by 14 days or more
3. Any Grade 3 or greater non-hematologic laboratory value if either:
  - The laboratory abnormality persists for >48 hrs despite supportive treatment, or
  - The abnormality leads to hospitalization
4. Hematologic toxicity:
  - Grade 4 hematologic toxicity lasting ≥7 days, except thrombocytopenia:
    - Grade 4 thrombocytopenia of any duration

- Grade 3 thrombocytopenia associated with clinically significant bleeding
- Grade 3 or greater febrile neutropenia lasting >48 hours despite adequate treatment:

CC1 - This section contained Clinical Outcome Assessment data collection questionnaires or indices, which are protected by third party copyright laws and therefore have been excluded.

- Grade 4 Thrombocytopenia <25,000/mm^3 if platelet transfusion is required.
- 5. Nephrotoxicity requiring dialysis, and not considered to be related due to disease under study (ie. myeloma) progression based on investigator's assessment.
- 6. Liver toxicity meeting pre-specified GSK liver stopping criteria
- 7. Prolonged delay (>14 days) in initiating Cycle 2 due to any treatment (pembrolizumab or GSK2857916) related toxicity, with the exception of Grade 1-2 corneal events (GSK grading scale for GSK2857916 treatment related corneal events)
- 8. Any treatment-related toxicity that causes the participant to discontinue treatment during Cycle 1.
- 9. Any other toxicity considered to be dose-limiting that occurs beyond 21 days will be considered in the selection of the dose to recommend for expansion cohorts.
- 10. Any other event which in the judgment of the investigator and GSK Medical Monitor is considered to be a DLT

A subject who develops a DLT will be allowed to continue on study treatment if the toxicity did not meet predefined stopping criteria and recovered to  $\leq$ Grade 1 within 14 days, or after a longer recovery period if the investigator and medical monitor agree that for a given subject the potential benefits may outweigh the risks.

**Reason for change:** Update to DLT language based on FDA comments and revisions to the GSK and Merck standard language.

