**New Table 1 Dose-Escalation Monitoring Rules for Part 1 Using the mTPI Method**  
**Dose finding Criteria for the Modified Toxicity Probability Interval Dose Finding**

Number of DLTs Toxicities	Number of Subjects treated at current dose					
	1	2	3	4	5	6
0	E	E	E	E	E	E
1	D	S	S	S	S	E
2	DU	D	S	S	S	S
3		DU	DU	D	S	
4			DU	DU	DU	
5				DU	DU	
6					DU	

The table was generated based on a beta/binomial model and precalculated before trial initiation. The letters in different colors are computed based on the decision rules under the mTPI method and represent different dose-finding actions. In addition to actions de-escalate the dose (D), stay at the same dose (S), and escalate the dose (E), the table includes action unacceptable toxicity (DU), which is defined as the execution of the dose-exclusion rule in mTPI. Excerpted from Ji et al . [Ji, 2010].

After each cohort, the BLRM will be used to calculate the posterior probabilities of DLT rate for all potential doses of GSK2857916 in combination with pembrolizumab lying within four toxicity intervals (under dosing, target dose range, excessive toxicity, and unacceptable toxicity). The four DLT toxicity intervals are defined as follows:

[0%, 16%) Underdosing

[16%, 33%) Target toxicity

[33%, 60%) Excessive toxicity

[60%, 100%) Unacceptable toxicity

The recommended dose for next cohort will be based on the following criteria: dose with the highest posterior probability of DLT rate lying in the target toxicity interval with the additional requirement that the sum of the posterior probabilities of the DLT rate lying in the excessive toxicity or unacceptable toxicity range is less than 25%. Selection of the next dose cohort to be enrolled is also subject to the constraint that the next dose level can be no more than two times that of the current dose level. Note that de-escalation as well as escalation is possible using this method.

The DLT observation period for subjects in Part 1 is 21 days after the first dose of the study treatment. The complete safety data from DLT observation period of at least 3 subjects are needed for dose escalation decisions. Subjects who have only received GSK2857916 or have been withdrawn from the study for reasons other than toxicity but prior to completion of DLT observation period will be replaced.

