##### **Section 6.5.1. – Dose modifications and managementreductions for GSK2857916-related toxicity**

In individual cases where, in the judgement of an investigator, waiting a full planned Cycle (21 days) to resume treatment after delays due to toxicities would be detrimental to the subjects' health, the Medical Monitor should be contacted to discuss an earlier re-start. An earlier re-start may be considered only for subjects who have recovered from toxicity to Grade 1 or less. Dosing cannot occur more frequently than every 21 days ( $\pm 3$  days). In such cases, efficacy and safety assessments must remain every 3 weeks from the initial efficacy and safety assessments (Cycle 1 Day 1), which may result in 2 separate visits (1 for disease assessment [Table 8] and 1 for dosing [Table 9]).

If GSK2857916 is held or discontinued for any toxicity, pembrolizumab is to be held or discontinued.

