**Table 9 Time and Events Table: Part 1 and Part 2 – On Study Assessments with Dosing Days (Cycles)**

Study Assessments 	C1 Day 1 (W ee k 1)	C1 Day 8 (W ee k 2)	Day 1 of C2 – C35, (IF DOSING) Cycles = 21 days	Notes
			Safety	
Infusion Related Vital Signs (BP, HR, Body Temperature )			X 	
 
1. All assessments will apply to Part 1 and 2 unless stated otherwise. Assessments should be done prior to drug administration, unless otherwise specified. From Cycle 2, assessments can be performed +/- 3 days prior to the scheduled date unless otherwise specified.
 
2. Infusion vital signs must be assessed for each infusion (GSK2857916 and pembrolizumab) at: pre-dose (within 30 minutes prior to SOI); post each infusion (EOI); and 1 hour post EOI. On dosing days with PK sampling time points, vital signs should be assessed prior to PK samples being drawn.
 

Weight	X		X	
Pregnancy Test			X 	
CK-MB, Troponin		X	X 	
Spot Urine (albumin / creatinine ratio)	X  , 6		X 	
Tripplicate 12-lead ECG	X 	X	X 	
			PK and ADA	
Pharmacokinetics  for GSK2857916 and pembrolizumab	X	X	X 	
 
8. PK samples to be taken (in all subjects) for both GSK2857916 and pembrolizumab measurement: C1D1: pre-dose (within 30 mins prior to SOI GSK2857916), EOI GSK2857916 (<math>\pm</math>5 min), pre-dose pembrolizumab (within 10 min prior to SOI pembrolizumab), EOI pembrolizumab (<math>\pm</math>5 min), 4 h after GSK2857916 SOI (<math>\pm</math>15 min), 9 h OR 24 h after GSK2857916 SOI (<math>\pm</math>1 h) according to the subject's preference;
 
C1D4: one sample anytime;
 
C1D8 to C1D15: one sample anytime;
 
C2D1 and C5D1: pre-dose (within 30 min prior to SOI GSK2857916) and EOI GSK2857916 (<math>\pm</math>5 min), pre-dose pembrolizumab (within 10 min prior to SOI pembrolizumab), EOI pembrolizumab (<math>\pm</math>5 min);
 
C8D1 and C11D1: pre-dose (within 30 min prior to SOI
 

Immunogenicity (ADA)	X		X 	
			Biomarker	
Soluble BCMA	X 		X 	
Serum (cytokines/ chemokines)	X	X		
11				

Study Assessments 	C1 Da y 1 (W ee k 1)	C1 Da y 8 (W ee k 2)	Day 1 of C2 – C35. (IF DOSING) Cycles = 21 days	Notes

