Plasma-cfDNA	X			
GSK2857916; EOI GSK2857916 (<math>\pm</math>5 min); C14D1 and every 3 cycles thereafter (i.e., C17, 20, until EOT): pre-dose (within 30 min prior to SOI GSK2857916). In Cycle 1, in the event the pembrolizumab infusion is delayed by at least 24 h samples should also be taken prior to SOI pembrolizumab dose, at EOI pembrolizumab and at 2.5 h and 7 h post pembrolizumab SOI in addition to the time points listed above.
 
9. Pre-dose GSK2857916 C1 Day1 (week 1), C2, C5 and every 3 cycles thereafter (i.e., C8, C11,..) until EOT.
 
10. Serum sBCMA samples will be collected each cycle at pre-dose (within 30 minutes prior to SOI) and at each PK timepoint in cycle 1.
 
11. Collect cytokine serum sample at C1D1 at pre-dose (within 30 minutes prior to SOI), EOI of pembrolizumab (<math>\pm</math>5 min) (even when infusion is interrupted or halted), 4h after GSK2857916 SOI, 9h OR 24h after GSK2857916 SOI (<math>\pm</math>1 hr) according to the subject's preference; and at C1D8.

			Treatment	
Administration of GSK2857916 	X		Day 1 of each cycle	
12. A window of <math>\pm</math> 3 days is acceptable for administration of study treatment after C1. GSK2857916 will be administered first as IV infusion, followed by 1 hr rest period. Refer to SRM for details. Pembrolizumab will be administered as second, in a 30min infusion, 1 hr after GSK2857916 EOI, provided subject did not develop IRR requiring intervention. If planned Cycle treatment is delayed due to toxicities which have resolved, if in the judgement of the investigator, treatment needs to be initiated prior to next planned Cycle, this can be discussed with the medical monitor. Dosing cannot occur more frequently than every 21 days (<math>\pm</math>3 days).

Administration of pembrolizumab 	X		Day 1 of each cycle	

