### 31. Section 7. STUDY ASSESSMENTS AND PROCEDURES

Affected rows/items within tables are presented for changes in this section:

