11. Collect a cytokine/chemokine serum sample during at C1D1 at pre-dose (within 30 minutes prior to SOI belantamab mafodotin), EOI of pembrolizumab (within 30 minutes after EOI~~±5 min~~) (even when infusion is interrupted or halted), 4 h after belantamab mafodotin GSK2857916 SOI, 9 h ~~OR~~ 24 h after belantamab mafodotin GSK2857916 SOI ( $\pm 1$  h), according to the subject's preference; and at C1D8 (+3 days, on same day as PK sample collection) and pre-dose belantamab mafodotin (within 30 min prior to SOI) at C2D1 and C5D1.

12. Collect pre-dose belantamab mafodotin (within 30 min prior to SOI) at C1D1, at every 12 weeks thereafter (pre-dose belantamab mafodotin), and at every MRD assessment timepoint.

13. Collect pre-dose belantamab mafodotin (within 30 min prior to SOI) at C1D1, C1D8 (+3 days, on same day as PK sample collection), and pre-dose belantamab mafodotin (within 30 min prior to SOI) at C2D1 and C5D1.

14. Collect during C1D1 at pre-dose (within 30 minutes prior to SOI belantamab mafodotin), EOI of pembrolizumab (within 30 minutes after EOI) (even when infusion is interrupted or halted), 4 h after belantamab mafodotin SOI, 24 h after belantamab mafodotin SOI ( $\pm 1$  h); at C1D8 (+3 days, on same day as PK sample collection), and one pre-dose belantamab mafodotin (within 30 min prior to SOI) at C2D1 and C5D1.

17. Corneal management information:

- ~~Prophylaxis with steroid eye drops (such as prednisolone phosphate 1% or dexamethasone 0.1%) 1 drop QID starting from 1 day prior to infusion and continuing for a total of 7 consecutive days. If dosing delayed for a non corneal event, the prophylactic steroid drops can be stopped.~~
- Prophylactic preservative-free artificial tears must be administered in each eye at least 4-8 times daily beginning on Cycle 1 Day 1 until end of treatment.
- At the start of each infusion, subjects may apply cooling eye masks to their eyes for approximately 1 hour as long as tolerated.

Abbreviations:

PBMC = peripheral blood mononuclear cell

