#### 44. Section 9.4.1. Analysis Populations

... DLT Evaluable Population: will consist of subjects fulfilling the 'All Treated' population criteria during part 1 (Dose Escalation) and are followed up for a 21-day period or withdrawn within 21 days due to an AE meeting the definition of a DLT as defined in Section 4.2.3.1. ....

**Reason for change:** Addition of new population to be analyzed.

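### The text shown lets the Part 1 Cycle 2 dose be given on Days 19–21, before the 21-day DLT period closes, and leaves unclear whether a later event counts

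*Protocol*

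**What the plan says.** All of this wording comes from the protocol's summaries of changes.

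- **DLT period.** Section 4.2.3 states: "The DLT observation period for subjects in Part 1 is 21 days after the first dose of the study treatment". The synopsis DLT section (Amendment 1, item 8) gives the same 21 days and equates them with one cycle.
- **DLT definition.** The event must be "attributed (definitely, probably, or possibly) to the study therapy during the 21 day DLT observation period". The wording refers to the study therapy and not to a particular dose.
- **Dosing window.** The Table 9 dosing note says that a window of plus or minus "3 days is acceptable for administration of study treatment after C1". The table's title names both Part 1 and Part 2, and its first footnote applies it to both parts unless stated otherwise. No exception for Part 1 Cycle 2 is shown.
- **DLT Evaluable Population** (Section 9.4.1, Amendment 2). Subjects qualify if they "are followed up for a 21-day period or withdrawn within 21 days due to an AE meeting the definition of a DLT". Nothing is said about when the second dose is given.
- **State of the text.** The dosing note was footnote 12 in Amendment 1. In Amendment 2, footnote 12 is the cfDNA note ("Collect pre-dose belantamab mafodotin (within 30 min prior to SOI) at C1D1, at every 12 weeks thereafter"), so the dosing note must have been renumbered. Amendment 2 prints changed items only ("Affected rows/items within tables are presented for changes in this section") and shows no change to the dosing window. The Amendment 3 summary lists none either.

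**The concern.** Part 1 is the first clinical use of this combination. Its escalation rule reads DLT counts from cohorts of at least three subjects, so a single event moves a cohort from escalate (0/3) to stay (1/3). That count is meant to describe the first cycle. If a site uses the early side of the window, the subject is re-dosed before his or her own DLT observation is complete, and the last days of the period mix first-dose and second-dose exposure.

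The text then gives two answers for an event after that dose. By the calendar, the event lies within 21 days of the first dose and is attributable to study therapy, so it counts. By the cycle, the second dose has begun Cycle 2, so the one-cycle window has ended and the event does not count. Some DLT criteria are themselves worded by cycle (discontinuation during Cycle 1, delay in starting Cycle 2) and the general definition by days, so the two clocks separate once dosing is early.

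**Working it through.** **Calendar.** Inputs: 21-day cycle, ±3-day window after Cycle 1, first dose on Day 1.

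- Scheduled Cycle 2 Day 1 = 1 + 21 = Day 22. Cycle 1 on schedule is Days 1–21, which reproduces the protocol's equation of 21 days with one cycle.
- Earliest permitted second dose = 22 − 3 = Day 19; latest = 22 + 3 = Day 25.
- Permitted early days inside Days 1–21: Days 19, 20 and 21, at most 3/21 = 14.3% of the period.

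| Second dose on | First-dose-only days | DLT-period days on or after second dose |
|---|---|---|
| Day 19 | 18 | 3 |
| Day 20 | 19 | 2 |
| Day 21 | 20 | 1 |
| Day 22 (on schedule) | 21 | 0 |

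**Escalation rule.** Recomputing the mTPI rule with a Beta(1,1) prior and the target interval 25% to 35% gives 0/3 = escalate, 1/3 = stay and 3/3 = de-escalate and exclude, as in the protocol's worked examples. It gives 2/3 = de-escalate.

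**Effect on a cohort of three, if a second-dose event is counted.** The documents give no rate of early dosing and no rate of DLT-grade events shortly after a second dose. I assume a probability q of 1%, 2% or 5% per early-dosed subject. The true first-cycle DLT rate p is set at 30% (the centre of the mTPI target) and at 15% (an assumption). An early-dosed subject then has event probability t = 1 − (1 − p)(1 − q). With one of three subjects early:

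- P(0/3) = (1 − p)²(1 − t)
- P(1/3) = t(1 − p)² + 2p(1 − p)(1 − t)
- P(2/3 or 3/3) = the remainder

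Example, p = 15% and q = 5%: 1 − t = 0.85 × 0.95 = 0.8075, and P(0/3) = 0.85 × 0.85 × 0.8075 = 0.5834.

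| p | q | Escalate | Stay | De-escalate |
|---|---|---|---|---|
| 15% | 0 | 61.4% | 32.5% | 6.1% |
| 15% | 1% | 60.8% | 32.9% | 6.3% |
| 15% | 2% | 60.2% | 33.3% | 6.5% |
| 15% | 5% | 58.3% | 34.5% | 7.2% |
| 30% | 0 | 34.3% | 44.1% | 21.6% |
| 30% | 1% | 34.0% | 44.1% | 21.9% |
| 30% | 2% | 33.6% | 44.2% | 22.2% |
| 30% | 5% | 32.6% | 44.3% | 23.1% |

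Upper limit, all three subjects early and q = 5%: P(escalate) = 0.8075³ = 52.7% at p = 15%, and 0.665³ = 29.4% at p = 30%. The escalate column matters only below 3.4 mg/kg, which this study may not exceed.

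**The case against.** The best reply is that the current protocol body is not visible. What can be read is the amendment log. The last amendment it describes is dated 27 August 2021, while the closing signature page is dated 21 February 2022. An exception for Part 1 Cycle 2 may stand in the current text. This limit stands, and the point must be read with it.

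A reader might infer that Section 6.5.1 independently permits early dosing, because it says "Dosing cannot occur more frequently than every 21 days" and adds ±3 days. The context does not support that. The sentence limits how soon treatment may restart after a toxicity delay; it does not authorise an early dose in a subject who is on schedule. Only the Table 9 window supports the point.

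A reader might also count Day 22, taking 21 days after the first dose to run through that day. Day 22 is the scheduled dosing day, so any overlap there is not produced by the early window.

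A third tempting reading is that a second-dose event on Days 19–21 plainly meets the DLT definition. Equating 21 days with one cycle leaves that open, and the investigator must also judge the event clinically relevant and attributable.

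The other objections concern size, and they hold. Several DLT criteria require persistence (at least 7 days, or more than 48 hours), so few events starting that late would qualify in the window. Twenty-one days of follow-up are still obtained. Assessments on dosing days come before the infusion. An acute second-dose event can usually be recognised from the infusion date. Escalation decisions weigh all safety data, and toxicity after Day 21 still informs the choice of dose.

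**Conclusion.** The point holds for the text shown. The Table 9 window allows a second dose on Days 19–21 in Part 1, inside the DLT period, and the text does not settle whether an event after it counts. It does not show a wrong escalation boundary or a loss of follow-up.

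The consequence is minor. The overlap is at most three days and arises only if a site doses early. The population's 21-day follow-up requirement points to the calendar reading, on which the error leans toward over-counting and is conservative for safety. With one of three subjects early, the chance of escalating drops by 0.6 to 3.1 percentage points at a true rate of 15% and by 0.3 to 1.7 points at 30%. These figures rest on assumed values of q and on the event being counted. The benefit of a change is a clean first-cycle DLT observation.

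**What to change.** In the Table 9 dosing footnote and in Section 4.2.3, state that in Part 1 the Cycle 2 Day 1 dose has a 0/+3-day window (not before Day 22) and is given only once the subject's Cycle 1 DLT assessment is complete. Keep ±3 days for later cycles and for Part 2.

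If early dosing occurs as a deviation, keep the subject in the DLT Evaluable Population, count any qualifying event, and flag its timing relative to the second dose at the dose-escalation review. If Part 1 dosing has already finished, that flag is the useful remaining step.

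The cost is one sentence in two places and up to three days less scheduling flexibility at one Part 1 visit. No subject is replaced and no event leaves the count.
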